10. STATISTICS

This is a descriptive safety study, where volunteers will be vaccinated with a single dose of ChAdOx1 RVF. Fifteen volunteers will be vaccinated in total. This sample size should allow an estimation to be made of the frequency and magnitude of outcome measures, rather than aiming to obtain statistical significance for differences between groups. Safety data will be presented according to frequency, severity and duration of adverse events.

The primary analysis for immunogenicity will be to assess the difference in magnitude of RVFV specific T-cell and antibody responses between the groups. We will assess vaccine immunogenicity by comparing the change in these immunological parameters from baseline to different time points.

Sample Size Selection

This is a descriptive phase I first in human trial that will balance the safety of volunteers with the aims to assess the vaccine's safety profile and immunogenicity after selected doses of the vaccines. The primary dose comparison will be between Groups 1, 2 and 3, which will have 3-6 subjects each. RVFV specific immunogenicity will be the key immunological readout assessed by a variety of immunological assays.

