3.10 Vaccine Development Strategy

A phase I clinical trial at a disease-endemic area (the MRC/Uganda Virus Research Unit, Entebbe) is planned following the ChAdOx1 RVF trial in Oxford. The optimal dose of ChAdOx1 RVF will be determined following the Oxford and Ugandan trials and, provided there are no safety concerns, phase II studies will be conducted in Uganda and Kenya.

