5.1 Rationale for Selected Doses

Doses to be administered in this trial have been selected on the basis of clinical experience with the ChAdOx1 adenovirus vector expressing different inserts and similar adenovirus vectored vaccines (eg. ChAd63).

A first-in-human dose escalation study using the ChAdOx1 vector encoding an influenza antigen (FLU004), safely administered ChAdOx1 NP+M1 at doses ranging from 5×10^8 to 5×10^{10} vp. Subsequent review of the data identified an optimal dose of 2.5×10^{10} vp balancing immunogenicity and reactogenicity. This dose has subsequently been given to over 175 volunteers in numerous larger phase 1 studies at the Jenner Institute (FLU005, TB034 VANCE01, ADVANCE and VAC067) and ChAdOx1 vectored vaccines have thus far demonstrated to be very well tolerated. The vast majority of AEs have been mild-moderate and there have been no SARs until this date in these studies.

Other ChAdOx1 vectored vaccines have been given at doses up to 5×10^{10} vp (MERS001, VAMBOX, CHIK001 and nCoV-19) whilst a different simian adenovirus vector (ChAd63) has been safely administered at doses up to 2×10^{11} vp with an optimal dose of 5×10^{10} vp, balancing immunogenicity and reactogenicity.

As this is a first-in-human assessment of the RVFV GnGc antigenic insert, the first dose of ChAdOx1 RVF proposed in this study (5×10^9 vp) is therefore 10 fold less than the expected tolerable dose of ChAdOx1 RVF (5×10^{10} vp). Doses will be gradually increased aiming to provide an optimal dose of ChAdOx1 RVF considering the tolerability, reactogenicity and immunogenicity profiles.

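### Does Section 10 contradict itself by disclaiming significant group differences and then making the between-group difference the primary immunogenicity analysis?

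*Protocol*

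**What the plan says.** Section 10 (Statistics) calls the trial a descriptive safety study. It gives the total, "Fifteen volunteers will be vaccinated in total", and says that this number should allow the frequency and magnitude of outcome measures to be estimated, "rather than aiming to obtain statistical significance for differences between groups".

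Two sentences follow on immunogenicity: "The primary analysis for immunogenicity will be to assess the difference in magnitude of RVFV specific T-cell and antibody responses between the groups", and "We will assess vaccine immunogenicity by comparing the change in these immunological parameters from baseline to different time points". Under Sample Size Selection the protocol adds: "The primary dose comparison will be between Groups 1, 2 and 3, which will have 3-6 subjects each".

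Three other places bear on the point. Sections 4.1 and 4.2 make safety the primary objective and immunogenicity the secondary one. Section 5.1 states the dose aim: "Doses will be gradually increased aiming to provide an optimal dose of ChAdOx1 RVF considering the tolerability, reactogenicity and immunogenicity profiles". Section 3.10 says when the dose is chosen: "The optimal dose of ChAdOx1 RVF will be determined following the Oxford and Ugandan trials".

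**The concern.** Read quickly, Section 10 seems to take back what it has just said. The design is not meant to show differences between groups, yet a difference between groups is the primary immunogenicity analysis and the three-group contrast is the primary dose comparison. One group has three volunteers. The three doses are ordered, and the text does not mention the ordering.

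If this meant pairwise significance tests, a non-significant result could be misread as no dose effect. An isolated significant result among several assays and time points could be misread as a finding. Immunogenicity by dose feeds the choice of dose for later trials, so either error would matter. A single trend over the ordered doses would then seem the better use of the same 15 volunteers.

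**Working it through.** **The plan's own figure.** Groups of 3, 6 and 6 (Section 5.2, Table 2) sum to 15, as stated. The protocol gives no significance level, power, effect size or SD, so there is no power calculation to reproduce. This fits a size chosen for description.

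**The sentences side by side.** The disclaimer concerns statistical significance. The immunogenicity sentence concerns a difference in magnitude. Group summaries and their ratios, with intervals, satisfy both. Nothing in Section 10 names a test, contrast or model, or says that the groups are to be treated as unordered. A difference between dose groups is compatible with a trend analysis. The word primary ranks this analysis within immunogenicity, which is itself a secondary objective. Choice of method, key assay, key time point and multiplicity is commonly left to the SAP, which is not at hand.

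**Precision.** The SD of 0.5 log10 is an assumption. The 95% limits on a fold ratio are 10^(t × SD × √(1/a + 1/b)).
- 3 versus 6: t(7 df) = 2.365, √(1/3 + 1/6) = 0.707, half-width 1.67 SD; 10^(1.67 × 0.5) ≈ 6.9.
- 6 versus 6: t(10 df) = 2.228, √(1/6 + 1/6) = 0.577, half-width 1.29 SD; 10^(1.286 × 0.5) ≈ 4.4.
- At an SD of 0.3 the factors are about 3.2 and 2.4.

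These limits are wide, as expected with 15 volunteers.

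**The claim that Group 1 could never differ significantly.** The smallest two-sided exact rank p for 3 versus 6 is 2/C(9,3) = 2/84 = 0.024. Three times this is 0.071. The bar therefore exists only for pairwise rank tests corrected over three pairs, and the protocol plans neither. Uncorrected, 0.024 lies below 0.05, and a t-test on log titres has no such floor.

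**Is a log-dose slope clearly better?** Simulated two-sided 5% power with n = 3/6/6, normal log10 responses, SD 0.5 (assumed):

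| Mean log10 response by group | Kruskal-Wallis | Slope on log10 dose |
|---|---|---|
| linear in log dose (0, 0.70, 1) | about 50% | about 75% |
| plateau (0, 0.85, 0.85) | about 41% | about 59% |
| top dose only (0, 0, 1) | about 82% | about 53% |
| late rise (0, 0.2, 1) | about 69% | about 63% |

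The slope loses in the last two rows although the top dose responds most. It is therefore wrong that the slope wins unless the top dose falls below the middle one.

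**What the slope measures.** On log10 dose relative to Group 1 the values are 0, 0.699 and 1, with mean (6 × 0.699 + 6 × 1)/15 = 0.680. Squared deviations, summed by group:
- Group 1: 3 × 0.680² = 1.386
- Group 2: 6 × 0.019² = 0.002
- Group 3: 6 × 0.320² = 0.616

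The total is 2.004, so the shares are 69%, 0.1% and 31%. The slope is almost exactly Group 3 minus Group 1 and says almost nothing about the two higher doses relative to each other. Its own 95% limits are 10^(2.160 × 0.5/√2.004) ≈ ×/÷ 5.8 per tenfold dose. Most of its gain over the rank test in the linear case comes from using one parametric contrast: a plain Group 1 versus Group 3 comparison with pooled SD has about 74% power there.

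**The dose-finding aim.** Section 5.1 rests the optimal dose on tolerability and reactogenicity as well as immunogenicity. Section 3.10 defers the choice until the Ugandan trial has also been done. The Oxford immunogenicity comparison is one input and is not asked to settle the dose.

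**The case for a change.** The strongest case for the concern is this. Section 10 uses the word primary for the between-group analysis and again for the dose comparison, and it does not repeat there that these are descriptive. A SAP written under this text inherits both the disclaimer and the comparison. Immunogenicity by dose does feed a later decision, and groups of this size cannot separate the doses reliably: 80% power at two-sided 5% needs a difference of about 2.3 SD for 3 versus 6 and 1.8 SD for 6 versus 6. One added sentence would cost nothing.

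The precision figures stand, given their assumptions. It is also true that Section 10 could have said once more that the comparison is descriptive and reported with intervals. But the section opens by saying what the sample size is for, and the later sentences are naturally read under that statement. The feared misreadings require significance tests that the text does not plan. What is left is detail of a kind that a SAP commonly supplies.

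**Conclusion.** The concern does not hold. Section 10 describes a descriptive trial whose immunogenicity results are to be compared between doses in magnitude, with no planned test and no claim of difference or equivalence. That the comparisons are unordered is inferred, not stated. The significance floor for Group 1 depends on a rank test and a correction that the protocol does not specify. The charge that the comparison cannot support the dose aim overlooks Section 3.10 and the criteria in Section 5.1.

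The small groups do limit what can be learned: about ×/÷ 6.9 and ×/÷ 4.4 at an assumed SD of 0.5 log10. The protocol's stated purpose already allows for that. Replacing group differences with a log-dose slope is a trade-off that turns on the unknown shape of the dose response: roughly 25 points of power gained if it is linear in log dose, and roughly 29 lost if only the top dose responds. All power and interval figures rest on assumed SDs and mean patterns, since the protocol gives none. The reading of the text does not depend on them.

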11. DATA MANAGEMENT

11.1 Data Handling

The Chief Investigator will be responsible for all data that accrues from the study. The data will be entered into the volunteers' CRFs in a paper and/or electronic format (using OpenClinica™ database). Electronic data will be stored on secure servers which are outsourced by OpenClinica™. Data will be entered in a web browser on PCs in the CCVTM building and then transferred to the OpenClinica Database by encrypted (Https) transfer. OpenClinica™ meets FDA part 11B standards. This includes safety data, laboratory data (both clinical and immunological) and outcome data.

Adverse event data will also be entered onto electronic or paper diaries by the volunteer

11.2 Record Keeping

The Investigators will maintain appropriate medical and research records for this trial, in compliance with GCP and regulatory and institutional requirements for the protection of confidentiality of volunteers. The Chief Investigator, co-Investigators and clinical research nurses will have access to records. The Investigators will permit authorised representatives of the Sponsor(s), as well as ethical and regulatory agencies to examine (and when required by applicable law, to copy) clinical records for the purposes of quality assurance reviews, audits and evaluation of the study safety and progress.

With the volunteers' consent, we will keep their contact details after participation in the study is complete, so we may inform them of opportunities to participate in future vaccine related research. This will be entirely optional and participation in this study will not be affected by their decision to allow or not allow storage of their contact details beyond participation in this trial. Details will be stored electronically on a secure server and only authorised individuals at the CCVTM will have access to it. We will not, under any circumstances, share their contact details with any third party institutions without their permission. Volunteers will be informed that being contacted does not oblige them to agree to take part in future research and they can ask us to have their contact details removed from our database at any time.

11.3 Source Data and Case Report Forms (CRFs)

All protocol-required information will be collected in CRFs designed by the Investigators. All source documents will be filed in the CRF. Source documents are original documents, data, and records from which the volunteer's CRF data are obtained. For this study, these will include, but are not limited to, volunteer consent form, blood results, GP response letters, laboratory records, diaries, and correspondence. In the majority of cases, CRF entries will be considered source data as the CRF is the site of the original recording (i.e. there is no other written or electronic record of data). In this study this will include, but is not limited to medical

history, medication records, vital signs, physical examination records, urine assessments, blood results, adverse event data and details of vaccinations. All source data and volunteer CRFs will be stored securely.

11.4 Data Protection

The study protocol, documentation, data and all other information generated will be held in strict confidence. No information concerning the study or the data will be released to any unauthorised third party, without prior written approval of the sponsor.

11.5 Data Quality

Data collection tools will undergo appropriate validation to ensure that data is collected accurately and completely. Datasets provided for analysis will be subject to quality control processes to ensure analysed data is a true reflection of the source data.

Trial data will be managed in compliance with local data management SOPs (including the overarching SOP OVC007 Data and Database Management). If additional, study specific information is required, an approved Data Management Plan will be implemented.

The trial will comply with the General Data Protection Regulation (GDPR) and Data Protection Act 2018, which requires data to be de-identified as soon as it is practical to do so.

11.6 Archiving

Study data may be stored electronically on a secure server, and paper notes will be kept in a key-locked filing cabinet at the CCVTM – Churchill Hospital, University of Oxford. All essential documents will be retained for a minimum of 5 years after the study has finished. The need to store study data for longer in relation to licensing of the vaccine will be subject to ongoing review. For effective vaccines that may be licensed, we may store research data securely at the University of Oxford for at least 15 years after the end of the study, subject to adjustments in clinical trials regulations. Participants' bank details will be stored for 7 years in line with University of Oxford financial policy.

General archiving procedures will be conducted in compliance to SOP OVC020 Archiving.

12. QUALITY CONTROL AND QUALITY ASSURANCE PROCEDURES

12.1 Investigator procedures

Approved site-specific standard operating procedures (SOPs) will be used at all clinical and laboratory sites.

12.2 Monitoring

Monitoring will be performed according to the principles of GCP by Clinical Trials Research Governance (CTRG). Following written SOPs, the monitors will verify that the clinical trial is conducted and data are generated, documented and reported in compliance with the protocol, GCP and the applicable regulatory requirements. The Investigator sites will provide direct access to all trial related source data/documents and reports for the purpose of monitoring and auditing by the Sponsor and inspection by local and regulatory authorities.

12.3 Protocol deviation

Any deviations from the protocol will be documented in a protocol deviation form and filed in the trial master file. Each deviation will be assessed as to its impact on volunteer safety and study conduct. Significant deviations will be listed in the end of study report.

12.4 Audit & inspection

The QA manager conducts systems based internal audits to check that trials are being conducted according to local procedures and in compliance with GCP and applicable regulations.

The Sponsor, trial sites, and ethical committee(s) may carry out audit to ensure compliance with the protocol, GCP and appropriate regulations.

GCP inspections may also be undertaken by the MHRA to ensure compliance with protocol and the Medicines for Human Use (Clinical Trials) Regulations 2004, as amended. The Sponsor will assist in any inspections and will support the response to the MHRA as part of the inspection procedure.

13. SERIOUS BREACHES

The Medicines for Human Use (Clinical Trials) Regulations contain a requirement for the notification of "serious breaches" to the MHRA within 7 days of the Sponsor becoming aware of the breach.

A serious breach is defined as "A breach of GCP or the trial protocol which is likely to effect to a significant degree

- (a) the safety or physical or mental integrity of the subjects of the trial; or
- (b) the scientific value of the trial".

In the event that a serious breach is suspected the Sponsor will be informed within one working day.

14. ETHICS AND REGULATORY CONSIDERATIONS

14.1 Declaration of Helsinki

The Investigators will ensure that this study is conducted according to the principles of the current revision of the Declaration of Helsinki.

14.2 Guidelines for Good Clinical Practice

The Investigators will ensure that this study is conducted in full conformity with the Good Clinical Practice (GCP).

14.3 Approvals

The protocol, informed consent form, participant information sheet and any proposed advertising material will be submitted to an appropriate Research Ethics Committee (REC), HRA (where required), regulatory authorities (MHRA in the UK), and host institution(s) for written approval.

The Investigator will submit and, where necessary, obtain approval from the above parties for all substantial amendments to the original approved documents.

No substantial amendments to this protocol will be made without consultation with, and agreement of, the Sponsor. Any substantial amendments to the trial that appear necessary during the course of the trial must be discussed by the Investigator and Sponsor concurrently. If agreement is reached concerning the need for an amendment, it will be produced in writing by the Chief Investigator and will be made a formal part of the protocol following ethical and regulatory approval.

The Investigator is responsible for ensuring that changes to an approved trial, during the period for which regulatory and ethical committee(s) approval has already been given, are not initiated without regulatory and ethical committee(s)' review and approval except to eliminate apparent immediate hazards to the subject.

14.4 Volunteer Confidentiality

All data will be anonymised: volunteer data will be identified by a unique study number in the CRF and database. A separate confidential file containing identifiable information will be stored in a secured location in accordance with the relevant data protection legislation. Only the Sponsor representative, Investigators, the clinical monitor, the REC and the MHRA will have access to the records. Photographs taken of vaccination sites (if required, with the volunteer's written, informed consent) will not include the volunteer's face and will be identified by the date, trial code and subject's unique identifier. Once developed, photographs will be stored as confidential records, as above. This material may be shown to other professional staff, used for educational purposes, or included in a scientific publication.

15. FINANCING AND INSURANCE

15.1 Financing

The study is funded by the UK Biotechnology and Biological Sciences Research Council (BBSRC) and the Medical Research Council (MRC)/Department of Health, through the UK Vaccines Network.

15.2 Insurance

The University has a specialist insurance policy in place, which would operate in the event of any participant suffering harm as a result of their involvement in the research (Newline Underwriting Management Ltd, at Lloyd's of London).

15.3 Compensation

Volunteers will be compensated for their time and for the inconvenience caused by procedures. They will be compensated £25 for attending the screening visit. For all other trial visits as outlined in Table 5, compensation will be calculated according to the following:

- Travel expenses:
 - £15 per visit. Where travel expenses are greater than £15 per visit because the volunteer lives outside the city of the trial site, the volunteer will be given further reimbursement to meet the cost of travel necessary for study visits.

- Inconvenience of blood tests:
 - £10 per blood donation

- Time required for visit:
 - £20 per hour

The total amount compensated will be approximately £370 depending on the exact number of visits and whether any repeat or additional visits are necessary.

16. CONTRACTUAL ARRANGEMENTS

An appropriate service level agreement will be put in place between the Sponsor and Oxford University Hospitals NHS Foundation Trust to cover arrangements for processing of blood samples.

17. PUBLICATION POLICY

The Investigators will be involved in reviewing drafts of the manuscripts, abstracts, press releases and any other publications arising from the study. Data from the study may also be used as part of a thesis for a PhD or MD.

18. DEVELOPMENT OF A NEW PRODUCT/PROCESS OR THE GENERATION OF INTELLECTUAL PROPERTY

Ownership of IP generated by employees of the University vests in the University. The protection and exploitation of any new IP is managed by the University's technology transfer office, Oxford University Innovations.

Appendix A: Oxford Laboratory Adverse Event Severity Grading

(Ox) Routine Haematology			Lab Range	Grade 0	Grade 1	Grade 2	Grade 3
Haemoglobin	Male	g/l	130 - 170	126 - 170	115 - 125	100 - 114	<100
	Female		120 - 150	114 - 150	105 - 113	90 - 104	<90
White Blood Cells	Elevated	x109/l	4.00 - 11.00	3.51 - 11.49	11.50 - 15.00	15.01 - 20.00	>20
	Low				2.50 - 3.50	1.50 - 2.49	<1.50
Platelets		x109/l	150 - 400	136 - 400	125 - 135	100 - 124	<100
Neutrophils		x109/l	2.0 - 7.0	1.5 - 7.0	1.00 - 1.49	0.50 - 0.99	<0.50
Lymphocytes		x109/l	1.0 - 4.0	1.0 - 4.0	0.75 - 0.99	0.50 - 0.74	<0.50
Eosinophils		x109/l	0.0 - 0.5	0.0 - 0.64	0.65 - 1.50	1.51 - 5.00	>5.00

Routine Biochemistry			Lab Range	Grade 0	Grade 1	Grade 2	Grade 3
Sodium	Elevated	mmol/l	135 - 145	135 - 146	147 - 148	149 - 150	>150
	Low				132 - 134	130 - 131	<130
Potassium	Elevated	mmol/l	3.5 - 5.0	3.4 - 5.0	5.1 - 5.2	5.3 - 5.4	>5.4
	Low				3.2 - 3.3	3.0 - 3.1	<3.0
Urea		mmol/l	2.5 - 7.4	2.5 - 8.1	8.2 - 8.9	9.0 - 11.0	>11.0
Creatinine		µmol/l	49 - 104	49 - 113	1.1-1.5*ULN 114 -156	>1.5-3.0*ULN 157 - 312	>3.0*ULN >312
					1.3-1.5*ULN 27 - 31	>1.5-2.0*ULN 32-42	>2.0*ULN >42
Bilirubin	Normal LFT	µmol/l	0 - 21	0 - 26	1.1-1.25*ULN 23 - 26	>1.25-1.5*ULN 27 - 31	>1.5-1.75*ULN >31
	Abnormal LFT		0 - 21	0 - 22	1.25 - 2.5*ULN 56 - 112	>2.5 - 5.0*ULN 113 - 225	>5.0*ULN >225
			When accompanied by any increase in LFT				
ALT		IU/l	10 - 45	10 - 55	1.1 - 2.0*ULN 143 - 260	>2.0 - 3.0*ULN 261 - 390	>3.0*ULN >390
Alk Phosphatase		IU/l	30 - 130	30 - 142	1.25 - 2.5*ULN 56 - 112	>2.5 - 5.0*ULN 113 - 225	>5.0*ULN >225
Albumin		g/l	32 - 50	32 - 50	28 - 31	25 - 27	<25

Coagulation Studies							
Prothrombin time		s	9.0 - 12.0	9.0 - 13.1	1.10*ULN 13.2	>1.10 - 1.20*ULN 13.3 - 14.4	>1.2*ULN >14.4
	(APTT)				1.10 - 1.20*ULN 33.0 - 36.0	>1.20 - 1.40*ULN 36.1 - 42.0	>1.4*ULN >42.0
Activated Partial Thromboplastin Time		s	20.0 - 30.0	20.0 - 32.9			
Fibrinogen		g/l	1.5 - 4.0	1.5 - 4.0	1.25 - 1.49	1.0 - 1.24	<1.0

Other							
AST		IU/l			1.25 - 2.5*ULN 52 - 105	>2.5 - 5.0*ULN 106 - 210	>5.0*ULN >210
Aspartate transferase			15 - 42	15 - 51			
GGT		IU/l			1.25 - 2.5*ULN 51 - 100	>2.5 - 5.0*ULN 101 - 200	>5.0*ULN >200
Gamma-glytamyl transpeptidase			15 - 40	15 - 50			

VC027 Appendix (OUH - v3.0 27 Jul 2016)

Severity grading criteria for clinically significant laboratory abnormalities; adapted from FDA guidelines (1) using Oxford University Hospitals NHS Foundation Trust laboratory reference ranges.
